provided with a food bar and asked to consume the bar. After consumption, the participant will complete visual analog scales to rate the following: visual appeal, smell, taste, texture, aftertaste, and overall pleasantness.

Data Analysis: The visual analog scales will be reviewed and minimum thresholds will be set for each parameter. 6 out of 10 participants must rate the bar as acceptable to be considered a successful bar.

Phase 1 - Schedule of events

Test/Visit	Test Day
Taste Test	x
Visual Analog Scale	x
Adverse Events	x

Phase 2

Once an acceptable bar has been developed, phase 2 will begin.

Aim 3: Measure safety parameters (blood chemistry) pre and post bar consumption.

Aim 4: Measure bioactive compounds in the blood to determine absorption and PK parameters.

Study Design: 10 healthy participants will be enrolled into the study. The study will have a screening visit and a testing visit.

Inclusion:

1. Healthy males or females between 18 and 50 years of age inclusive.
2. BMI criteria 20-30 kg/m².

Exclusion:

1. Pregnant or currently lactating.
2. Taking any prescription medications.
3. Taking an OTC medications that cannot be stopped on testing day
4. Allergic to any ingredients contained in the bar.
5. A participant in phase 1 of the study.

56 Other conditions or situations that would interfere with the study or the participant's safety as determined by the investigators.

Screening visit: Participants will come to the screening visit having had nothing but water from 10pm the prior night. They will sign an informed consent after having all questions answered, complete a medical history questionnaire, have blood pressure, pulse, weight and height measured, and have blood drawn from an arm vein for a chemistry panel (less 2 teaspoons of blood). The chemistry panel will provide basic health information and participants may be excluded for abnormal lab values as determined by the study physician.

Testing Visit: The testing day will occur within 30 days of the screening visit. The participants will come back to the Pennington Biomedical Outpatient Clinic having had nothing but water from 10pm the prior night for the

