testing visit. Each participant will be provided with a food bar and asked to consume the bar within 10 minutes. Blood samples will be taken prior to consumption of the bar (-10 minutes), baseline (time 0 after the bar is consumed) and at times 30, 60, 120 and 180 minutes post ingestion of the bar for glucose, insulin and bioactives.

Statistics: Normally distributed data will be analyzed by t-test and non-parametric data will be analyzed by chi squared testing or another appropriate statistical test.

Phase 2 - Schedule of events

Test/Visit	Screening	Test Day
Consent	x	
Chemistry Panel	x	x
Medical Questionnaire	x	
BP, Pulse & weight	x	
Height	x	
Bioactives		x
Taste Test		x
Visual Analog Scale		x
Adverse Events		x

Acceptability Visual Analog Questionnaire

Palatability Ratings

Smell

Taste

Texture

Aftertaste

Pleasant/Unpleasant (Please check)

Overall Pleasantness

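### A pre-to-post test on group means is the wrong tool for Aim 3: fasted-versus-fed, single-arm data call for a per-participant shift table

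*Combined protocol and SAP*

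**What the plan says.** All references are to the combined protocol and SAP.

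- **Objective and Aim 3.** The Objective includes that the bar be safe to eat. The Phase 2 aim on safety is "Aim 3: Measure safety parameters (blood chemistry) pre and post bar consumption". No limit, reference range or rule says how a chemistry change is to be read. Acceptability in Phase 1, by contrast, has a success rule of 6 out of 10.
- **Design.** Phase 2, Study Design: "10 healthy participants will be enrolled into the study. The study will have a screening visit and a testing visit". No control bar, crossover or fasting control is described.
- **State at sampling.** Participants attend both the screening and the testing visit "having had nothing but water from 10pm the prior night". The bar is planned at 250 kcal with 40% of energy from fat (Objective and Aim 1).
- **Samples.** The timed test-day draws, at -10, 0, 30, 60, 120 and 180 minutes, end at "180 minutes post ingestion of the bar for glucose, insulin and bioactives". The Phase 2 schedule marks a chemistry panel at screening and on the test day, with no clock time. It also marks adverse events on the test day.
- **Analysis.** Phase 2, Statistics: "Normally distributed data will be analyzed by t-test". Other data get a chi-squared test or some other suitable test. Endpoint, pairing, significance level and sidedness are not given.

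**The concern.** Any pre-bar value is fasted and any post-bar value is fed. For analytes that respond to eating (glucose, insulin and, if they are on the panel, lipids), a change is expected after any bar of this kind, with or without 5011-Nutrasorb. The null hypothesis of a pre-to-post t-test is that the mean does not change, which is not the safety question.

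The test could mislead in three ways:

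- A significant result may show only that people ate.
- A non-significant result in 10 people is weak evidence and could be read as reassurance.
- A mean can hide one participant with a clearly abnormal value, which is what a small safety assessment most needs to find.

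Glucose and insulin raise a related problem. They are drawn six times on the test day, but no aim names them. Without a control bar their curves cannot be divided between the ingredient and the meal.

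**Working it through.** **1. The bar (Aim 1).** The stated components give 120 + 100 + 30 = 250 kcal, and 100/250 = 40% from fat, so the plan's own figures reproduce. One entry needs reconciling: 20 g of fat at an assumed 9 kcal/g is 180 kcal, not 100, which would make the total 120 + 180 + 30 = 330 kcal. The argument below does not depend on which is meant.

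**2. Which samples are compared.** There are two candidates for the pre-bar panel: the screening panel and a test-day sample before the bar. Both are fasted. If screening is used, time between visits is a further confounder, since "The testing day will occur within 30 days of the screening visit". The timed draws do not list the chemistry panel, so the documents do not establish when, or whether, a post-bar panel is drawn.

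**3. How often the test flags a pure meal effect.** The documents give no expected shift, SD or significance level. Assume a paired t-test, n = 10 and two-sided 5%, with a meal-only mean shift of d SDs of the within-person change and no effect of the ingredient. The test statistic is then noncentral t with 9 df and noncentrality d × √10, and the critical value is 2.262.

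| d (SD) | d × √10 | Chance of significance |
|---|---|---|
| 0.25 | 0.79 | 0.109 |
| 0.5 | 1.58 | 0.293 |
| 0.75 | 2.37 | 0.562 |
| 1.0 | 3.16 | 0.803 |
| 1.5 | 4.74 | 0.987 |
| 2.0 | 6.32 | 0.9998 |

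With a matched control bar in the same people, the shared meal effect would cancel and the rate would return to 0.05.

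**4. What a non-significant result is worth.** The same test reaches 80% power only at a shift of about 1.0 SD. For individual abnormalities, 0 of 10 leaves an upper one-sided 95% limit of 1 − 0.05^(1/10) = 25.9%. If the true risk were 10%, the chance of seeing at least one case would be 1 − 0.9^10 = 65%.

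**5. One abnormal participant.** Suppose one person changes by X and nine do not change.

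- Mean change = X/10.
- Variance = [(0.9X)² + 9 × (0.1X)²]/9 = 0.1X².
- Standard error = √(0.1X²/10) = X/10.
- Absolute value of t = (X/10)/(X/10) = 1.

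This is below 2.262 however large X is. In this simplified case the group test cannot flag a single abnormal response, whereas a per-participant table shows it directly.

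**The case against.** The strongest reply is that the plan does not do what is being criticised. Aim 3 says only that chemistry will be measured. The Statistics sentence is generic, names no endpoint and leaves room for another test. The Objective concerns the bar as eaten, so its meal effect is part of the exposure. Adverse events are collected, earlier safety studies of the ingredient are cited as background, and this is a 10-person pilot. The power figures are standard paired-t values at arbitrary effect sizes, and detecting a real fasted-to-fed shift is the test working as it should.

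Most of this stands, and it rules out three stronger readings that a reader might infer:

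- **That the plan makes the t-test its safety rule.** No section says so.
- **That the plan credits chemistry, glucose or insulin changes to 5011-Nutrasorb.** No section does.
- **That a single-arm study cannot inform safety at all.** Individual values, analytes little affected by a meal, and adverse events can all inform the safety of the bar as eaten.

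What does not fall away is that the Statistics sentence is the only analysis text for Phase 2. An analyst following it would test group means, and nothing in the plan offers a better way to read the chemistry.

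A second fair reply is that a shift table keeps the fasted-versus-fed contrast: an inert bar can also move a participant out of a range. That is correct, and the fix has to handle fed-state values explicitly.

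**Conclusion.** The point holds in a limited form. If the stated analysis is applied to pre-to-post group means, it will register ordinary meal effects in meal-sensitive analytes, it can miss an individual abnormality, and with 10 people it cannot support a safety conclusion when non-significant. It is therefore the wrong method for Aim 3. The samples themselves remain useful for a descriptive safety review, provided a post-bar chemistry panel is actually drawn.

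The single-arm, fasted-versus-fed structure comes directly from the documents. The flag rates in the table rest on an assumed paired two-sided 5% test and assumed shifts, so they show how the problem scales and predict nothing for a given analyte. Analytes that hardly respond to a meal are less affected. The plan should be changed on this point, but the change is to analysis and reporting and does not require a redesign.

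**What to change.** 1. State which samples are the pre- and post-bar chemistry panels, with clock times, and make the testing-visit text agree with the schedule of events.
2. Report Aim 3 as a per-participant pre-to-post shift table against laboratory reference ranges. Read meal-sensitive analytes against limits suited to the fed state, or describe them only.
3. Have the study physician review each new out-of-range value, and report these alongside adverse events.
4. State that the safety conclusion does not rest on the t-test or any other test of group means.
5. Present glucose and insulin as descriptive meal-response curves, and state that no change is attributed to 5011-Nutrasorb.

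The cost is protocol wording, one table and a little more reporting work, with no new participants. A post-bar chemistry panel is not an added cost of this fix, because Aim 3 already calls for one. The study gives up any inferential claim about a 5011 effect on glucose or insulin, which the single-arm design could not support. A matched control bar would be needed only if the sponsor wanted to make such a claim.

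### The Phase 2 sample called baseline is drawn after the bar has been eaten, and no analysis rule makes the pre-dose sample the reference

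*Combined protocol and SAP*

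**What the plan says.** All references are to Phase 2 of the combined protocol and SAP.

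- **Eating window (Testing Visit).** Each participant is "asked to consume the bar within 10 minutes". No minimum or fixed duration is given.
- **Pre-dose sample (Testing Visit).** "Blood samples will be taken prior to consumption of the bar (-10 minutes"). This sample is not called baseline.
- **Sample called baseline, and later samples (Testing Visit).** The remaining draws are at "baseline (time 0 after the bar is consumed) and at times 30, 60, 120 and 180 minutes post ingestion of the bar". The series is "for glucose, insulin and bioactives".
- **Purpose.** Aim 4 is to "Measure bioactive compounds in the blood to determine absorption and PK parameters". Aim 3 is to "Measure safety parameters (blood chemistry) pre and post bar consumption".
- **Analysis (Statistics).** One sentence allows a t-test, a chi-squared test or another suitable test. It does not say which sample is the reference for change, baseline correction or AUC.

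The document does not ask for the start of eating, the end of eating or the actual draw times to be recorded.

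**The concern.** A baseline for a response to a test food has to be taken before any of the food is eaten. Here the label sits on a sample taken once the whole bar is inside the participant, and the only sample free of exposure carries no such label. With no reference sample named under Statistics, an analyst following the text could reasonably subtract the sample that the text calls baseline.

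If that happened, any response already present at the end of eating would be removed from every later value in that participant. Cmax and AUC corrected in this way would be too low. The loss would vary with eating speed, because a slow eater has had longer to absorb before time 0. All three analytes come from the same series, so all three are open to it.

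Unrecorded eating times cannot be recovered later. Without them, neither an elapsed-time PK calculation nor a check on the effect of eating speed is possible.

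**Working it through.** The plan states no figure for this, so there is nothing to reproduce. The check has three steps.

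**1. Timing, from the document alone.** Let D be the eating duration, 0 to 10 minutes. Time since first bite = nominal time + D.

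| Nominal draw (min) | Minutes since first bite | Spread as share of nominal time |
|---|---|---|
| 0 | 0-10 | not defined |
| 30 | 30-40 | 10/30 = 33.3% |
| 60 | 60-70 | 10/60 = 16.7% |
| 120 | 120-130 | 10/120 = 8.3% |
| 180 | 180-190 | 10/180 = 5.6% |

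The time-0 sample is thus up to 10 minutes into exposure. The -10 minute sample is stated to precede consumption. The text does not say whether -10 is counted from the start or the end of eating, but it is pre-exposure either way.

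**2. How much response the time-0 sample could hold.** This needs kinetics that the document does not give. I assume one compartment, first-order absorption (ka) and elimination (ke), no lag, intake spread evenly over D, and dose/volume set to 1. At the end of eating:

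C(D) = ka / [(ka − ke) × D] × [(1 − e^(−ke·D))/ke − (1 − e^(−ka·D))/ka]

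With D = 10 min = 1/6 h and three assumed pairs (per hour):

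| ka, ke | C at time 0 | Cmax (even intake) | Ratio |
|---|---|---|---|
| 1, 0.3 | 8.571 × (0.16257 − 0.15352) = 0.0776 | 0.597 | 13% |
| 2, 0.5 | 8.000 × (0.15991 − 0.14173) = 0.1454 | 0.629 | 23% |
| 3, 0.7 | 7.826 × (0.15731 − 0.13116) = 0.2047 | 0.641 | 32% |

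- For a 5-minute eater the ratios are 7%, 12% and 18%.
- Over a wider assumed range (absorption half-life 10-60 min, elimination half-life 90-240 min), a 10-minute eater has 9-36% with no lag.
- With a 10-minute lag the ratio is 0% in every scenario.

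Subtracting C(time 0) lowers Cmax by these fractions. It lowers AUC over the sampling window by a larger fraction, because the mean concentration is below Cmax. The model describes an absorbed compound. For glucose and insulin, which start above zero and are regulated, it supports only the direction of the error.

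**3. Whether the choice of clock origin matters.** I used the same three pairs at the nominal 30-minute draw and compared a 10-minute eater with instant intake:

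| ka, ke | Instant intake | Clock from last bite (the plan) | Clock from first bite |
|---|---|---|---|
| 1, 0.3 | 0.3631 | 0.4012 (+10.5%) | 0.3180 (−12.4%) |
| 2, 0.5 | 0.5479 | 0.5792 (+5.7%) | 0.5007 (−8.6%) |
| 3, 0.7 | 0.6281 | 0.6385 (+1.7%) | 0.5973 (−4.9%) |

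Both origins leave a difference tied to eating speed, and it is no smaller with the first bite as origin.

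**The case against.** The strongest reply is that nothing is lost. A true pre-dose sample is scheduled, so the correct baseline can be chosen at analysis whatever the label says. The plan specifies no change-from-baseline or baseline-corrected analysis, and Aim 3's before-and-after wording points to the pre-consumption sample. The stated objective is detectable serum levels within 6 hours, which a shift of 10 minutes hardly affects. Observed Tmax is in any case resolved only to the 30- to 60-minute gaps between draws.

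Most of this stands, and it limits the severity. It does not remove the point. The label contradicts its own definition, the reference sample is left open, and Aim 4 asks for PK parameters as well as detection.

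The reply also disposes of three stronger readings:

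- **That the draws fall at unequal times, an error of up to 33% at 30 minutes.** The plan counts from the end of eating, and on that clock nominal times are the same for everyone. The 33% is a spread measured from an origin that the plan does not use, and it falls to 5.6% by 180 minutes.
- **That time 0 ought to be the first bite.** Step 3 of the working gives no support for this.
- **That the time-0 sample of a 10-minute eater holds 25-58% of Cmax.** That range comes from the same assumed pairs with the whole bar counted as swallowed at the first bite, which cannot be so for someone still eating.

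**Conclusion.** The concern holds as a labelling and analysis-rule defect. The sample that the plan calls baseline is post-exposure, and nothing in the plan prevents its use as the reference. If it is used, about 13-32% of Cmax would be subtracted for a 10-minute eater, under assumed one-compartment kinetics with even intake and no lag. The loss would be smaller for faster eaters and about 0 if absorption lags 10 minutes or more. A lag is plausible with a solid high-fat bar, but the document has no data on it.

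A reader might infer that the plan will subtract the time-0 sample and that its results will be biased. The document does not say so; the bias is conditional on that use. Severity is minor to moderate for a 10-person pilot. The label is certain from the text; the size rests wholly on assumed kinetics.

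**What to change.** In the Phase 2 Testing Visit and Statistics text:

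1. Name the -10 minute sample as the only baseline for glucose, insulin and bioactives.
2. Describe the end-of-eating draw as the first post-dose sample and drop the word baseline from it.
3. State the clock origin, either first bite or last bite, and apply it to every participant. Say from which event the -10 is counted.
4. Record clock times of first bite, last bite and each draw.
5. Compute AUC, Tmax and any other time-based PK parameter from actual elapsed times. Compute any change from baseline or baseline-corrected value against the -10 minute sample.

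Possible wording for Statistics: *The sample drawn before the bar is eaten is the baseline for all analytes. The sample drawn at the end of eating is the first post-dose sample. PK parameters are computed from recorded times elapsed since [first bite / last bite].*

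The cost is a few lines of text, two extra clock times on the form with the draw times, and individual rather than nominal times in the analysis. It needs no extra blood, visits or participants. The recording has to be in place before testing starts; the baseline rule should be fixed before the data are analysed.

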Pilot Study Evaluating the Hedonic Acceptability and Absorption of the Bioactive Compounds of a 5011-Nutrasorb Bar (Russian Tarragon Nutrasorb)

February 12, 2020

Background: Based on previous safety studies with 5011-Nutrasorb, it was decided to develop 30g into a high fat bar that would be acceptable in taste and that would provide detectable levels of 5011 in the circulation.

Objective: 5011-Nutrasorb can be formulated into a high fat (40% kcal from fat) bar that is safe and acceptable for human consumption and is compatible with detectable serum levels of the identified bioactive compounds within 6 hours of consumption

Phase 1

Aim 1: Formulate a bar containing 30 g of 5011-Nutrasorb and 40% fat. The goal is to develop a bar containing the following:

30 g PMI 5011-Nutrasorb (120 kcal)

20 g fat (100 kcal)

Remainder kcal (30) from carbohydrate and flavorings

Total kcal of bar – 250 kcal

Aim 2: Determine by visual analog scales the acceptability of the bar.

Study Design: 10 healthy participants will be enrolled into the study. The study will have a single testing visit. Once all 10 people have completed the study, the visual analog scales will be reviewed. The study may be repeated with the same 10 participants two additional times in case the first or second product is not acceptable. If the initial bar is not acceptable, the fat source and/or flavoring may be modified to improve acceptability.

Inclusion:

1. Healthy males or females between 18 and 50 years of age inclusive.
2. BMI 20-30 kg/m².

Exclusion:

1. Pregnant or currently lactating.
2. Taking any prescription medications.
3. Taking any OTC medications that cannot be stopped for test days.
4. Allergic to any ingredients contained in the bar.
5. Other conditions or situations that would interfere with the study or the participant's safety as determined by the investigators.

Testing Visit: The participants will come to the Pennington Biomedical Outpatient Clinic having had nothing but water from 10pm the prior night for the taste test. After appropriate written consent, participants will have their height and weight measured, BMI calculated and vital signs measured. Participants will also be asked about any medications that they may be taking. Following completion of these procedures, each participant will be

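### Aim 4 asks for PK estimates in one group of 10, but the Phase 2 statistics provide only tests, chosen by a normality judgement that 10 values cannot support

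*Combined protocol and SAP*

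**What the plan says.** Phase 2 is a single group: "10 healthy participants will be enrolled into the study. The study will have a screening visit and a testing visit". Its fourth aim is to "Measure bioactive compounds in the blood to determine absorption and PK parameters". Under Testing Visit, blood is drawn 10 minutes before the bar, at time 0 (after the bar has been eaten), and then "at times 30, 60, 120 and 180 minutes post ingestion of the bar for glucose, insulin and bioactives".

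The Phase 2 Statistics paragraph is one sentence with two branches. The first is "Normally distributed data will be analyzed by t-test". The second is "non-parametric data will be analyzed by chi squared testing or another appropriate statistical test".

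Nothing else in the document describes the analysis of the bioactive concentrations. It names no PK parameter, summary statistic, confidence interval, scale of analysis, contrast, significance level or way of judging normality. The Objective at the head of the document asks for a bar "compatible with detectable serum levels of the identified bioactive compounds within 6 hours of consumption".

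**The concern.** There are two linked problems.

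1. **Aim and analysis do not match.** Determining PK parameters in one group is an estimation task. Cmax, Tmax and AUC have no comparator here, and a significance test does not produce them. Neither branch of the sentence supplies an estimate or a statement of its precision.

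2. **The method depends on how the data look.** The branch is decided by whether the data are normally distributed. With 10 values, a right-skewed distribution will often look normal. Concentration measures are often right-skewed. The samples that look normal tend to be those in which the long upper tail did not show itself. An arithmetic mean with a symmetric interval from such a sample is likely to understate both the mean and its uncertainty.

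At stake are the exposure estimates that the pilot would hand on to later work.

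**Working it through.** **Aim against analysis.** This part needs no arithmetic. Aim 4 needs, for each compound, a value of each exposure measure per participant, a group summary and its precision. The Statistics sentence gives a t-test in one branch, and chi-squared or an unnamed test in the other. None of the needed quantities appears.

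**Can 10 values support the choice of branch?** The plan has no figure to reproduce, so this is an illustration.

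Input from the document: n = 10, one group.

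Inputs assumed, because the document is silent:
- exposure is log-normal, with between-participant CV from 20% to 150%;
- normality is judged by Shapiro-Wilk at the 5% level;
- values that pass are left untransformed and summarised by a two-sided 95% t-interval.

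Formulas:
- Log-scale SD: s = sqrt(ln(1 + CV²)). At CV 50%, s = sqrt(ln 1.25) = 0.472. At CV 100%, s = sqrt(ln 2) = 0.833.
- True arithmetic mean, with the geometric mean set to 1: exp(s²/2) = sqrt(1 + CV²). This is 1.118 at CV 50% and 1.414 at CV 100%.
- Raw-scale interval: mean ± t × SD/√10, with t on 9 degrees of freedom = 2.262.
- Log-scale interval: the same formula on the logged values, back-transformed to the geometric mean.

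Results from 40,000 simulated samples per CV (Monte Carlo error about 0.1 to 0.4 percentage points). The last three columns are restricted to samples that pass the check.

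| CV | Pass the check | Raw-scale coverage, all samples | Raw-scale coverage, if passed | Interval wholly below true mean | Interval wholly above true mean |
|---|---|---|---|---|---|
| 20% | 92.0% | 94.4% | 94.3% | 4.2% | 1.5% |
| 30% | 87.7% | 93.9% | 93.5% | 5.3% | 1.2% |
| 50% | 77.1% | 92.4% | 91.1% | 8.1% | 0.8% |
| 70% | 65.2% | 90.4% | 87.5% | 11.9% | 0.7% |
| 100% | 51.3% | 87.0% | 79.9% | 19.8% | 0.3% |
| 150% | 34.5% | 81.9% | 66.5% | 33.2% | 0.2% |

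Four things follow:
- The shortfall from 95% after a passed check is 95 − 93.5 = 1.5 points at CV 30%, 95 − 91.1 = 3.9 points at CV 50%, and 95 − 79.9 = 15.1 points at CV 100%.
- The check makes matters worse than always using the t-interval: by 92.4 − 91.1 = 1.3 points at CV 50%, and by 87.0 − 79.9 = 7.1 points at CV 100%.
- The intervals are too short. Among passing samples, the median width relative to the width using the true SD is 0.82 at CV 50% and 0.57 at CV 100%.
- If the data really are normal, coverage is 94.9% with or without the check, so the skewness drives the result.

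**The alternative.** A pre-specified log-scale interval with no check covers the geometric mean 94.7% to 95.1% of the time at every CV above, with misses balanced at about 2.5% on each side.

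**Detectability.** A one-sample t-test of exposure against zero rejects in 100% of samples up to CV 50%, 99.8% at CV 70%, 96.6% at CV 100% and 84.7% at CV 150%.

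**The case against.** The strongest reply is that the coverage figures describe a procedure the plan does not contain. Much of that stands.

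- A reader might infer that a t-test on untransformed concentrations is the only planned analysis. The text does not support this. The same sentence opens a second, unrestricted route for other data, and it neither plans nor excludes a log transformation.
- A reader might infer that the trial will report intervals that are too short. The plan contains no intervals. The coverage loss arises only if the t-test becomes the basis for estimation.
- The plan names no normality check. The classification could be made in advance for each variable, or by eye. Shapiro-Wilk at 5% is an assumption, as are log-normality and the CVs.
- Skewed samples do not always pass. At CV 150%, where coverage is worst, only 34.5% do. Misses are mainly, not wholly, on the low side.
- The roughly 95% coverage of the log-scale interval is for the geometric mean, a different target, and it follows almost by construction from log-normal data. With the arithmetic mean kept as the target, a log-scale (Cox-type) interval covers 94.9% at CV 50% and 94.1% at CV 100%. Its misses at CV 100% are still uneven, with 5.4% below and 0.5% above.
- The simulation has no unquantifiable values, although detectability is an open question in this trial.
- No sample size or decision rule in the document uses an exposure interval.

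None of this supplies what Aim 4 lacks. The open wording of the second branch still offers only a test, and the silence on scale and interval is itself the gap.

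**Conclusion.** The point holds as a mismatch between aim and analysis, together with a weak rule for choosing the method. That Aim 4 has no planned estimate, interval or scale follows from the text alone. That 10 values cannot reliably show normality is general, and its size is illustrated above.

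The numerical consequence is conditional on log-normal exposure, a 5% Shapiro-Wilk check, untransformed values and a t-interval used for estimation. On those assumptions the loss of coverage is trivial to small at CV 20% to 30%, about 4 points at CV 50% and about 15 points at CV 100%. The document gives no CV, so it cannot be said where in this range the trial lies.

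A reader might go further and infer that the Objective is compromised. The document does not support that. The Objective asks for detectable levels, and up to CV 100% the simulated test against zero rarely fails. The harm is to the exposure estimates. The change should be made, but it is not a reason to hold the study.

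**What to change.** For Aim 4, replace the normality-based choice with pre-specified estimation:

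- For each compound, derive each participant's observed Cmax, Tmax and AUC from 0 to 180 minutes.
- Report Cmax and AUC as geometric mean, geometric CV and 95% CI from a t-interval on the log scale. Report Tmax as median and range.
- Report the number of participants with any quantifiable post-dose sample, with an exact 95% CI. State that the geometric means are conditional on quantifiable exposure.
- State in advance how values below quantification within a profile are handled. Do the same for the sample taken 10 minutes before the bar, which is the only pre-dose sample because time 0 falls after the bar is eaten.

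No participant, sample or visit is added. The cost is new wording in the Statistics paragraph, a little more analysis work to set and apply the quantification rules, and summaries that are geometric rather than arithmetic means.
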